6.4.1 Spirometry

The following spirometric assessments will be made:

- Forced expiratory volume in one second (FEV₁)
- Forced Vital Capacity (FVC)
- Forced Expiratory Flow between 25% and 75% of Forced Vital Capacity (FEF₂₅₋₇₅)

Spirometric assessments will be measured at Visit 201/202, 204, 207, 214 and EOT (if applicable) as indicated in [Table 6-2](#).

Trough FEV₁ is defined as the mean of the two FEV₁ values measured at 23 hr 15 min and 23 hr 45 min after the evening dose taken at the site.

Pre-dose FEV₁ is defined as the mean of the two FEV₁ values measured at -45 min and -15 min prior to evening dose.

Please refer to the Spirometry Guidance in [Appendix 4](#) and [Table 6-2](#) for full details on scheduling and performing spirometry.

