2.6.1.1 Variables

2.6.1.1.1 Primary variable trough FEV₁

Trough FEV₁ is defined as the average of the two FEV₁ measurements taken 23 hr 15 min and 23 hr 45 min post-evening dose. Trough measurements will be done at Day 2, Day 184 (Week 26, the primary endpoint) and Day 365.

If any of the 23 hr 15 min and 23 hr 45 min values contributing to the trough FEV₁ are collected within 3 months of a single depot corticosteroid injection, or within 7 days of systemic corticosteroid use, or within 6 hours of rescue medication, or if actual measurement times are outside of the 22 - 25 hour post-evening dose time window for o.d. regimens (or 8 – 13 hour post-morning dose time window for b.i.d. regimens), then the individual FEV₁ value will be set to missing. If one of the two values is missing (or set to missing) then the remaining non-missing value will be taken as trough FEV₁. If both values are missing, then trough FEV₁ will be missing.

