2.6.1.2 Statistical model, hypothesis, and method of analysis

Primary variable

The primary objective to demonstrate superiority of either QMF149 150/160 µg to MF 400 µg or QMF149 150/320 µg to MF 800 µg in terms of trough FEV₁ after 26 weeks of treatment will be evaluated by testing the following null hypotheses (H₀) versus the alternative hypotheses (H_a):

H₀₁: QMF149 150/160 µg is equal to MF 400 µg

versus

H_{a1}: QMF149 150/160 µg is not equal to MF 400 µg

and

H₀₂: QMF149 150/320 µg is equal to MF 800 µg

versus

H_{a2}: QMF149 150/320 µg is not equal to MF 800 µg

The primary variable, trough FEV₁ at Week 26, will be analyzed using a mixed model for repeated measures (MMRM) on the FAS. The model will contain treatment, age group (12 to 17, or ≥ 18 years), region (Eastern Europe, Western Europe, India, Japan, other Asia, rest of world), visit (Days 2, 184, and 365), and treatment-by-visit interaction as fixed effects with baseline FEV₁ measurement, baseline-by-visit interaction, FEV₁ prior to inhalation and FEV₁ within 15 to 30 min post inhalation of salbutamol/albuterol (components of short acting beta-2 agonist (SABA) reversibility) as covariates, and center nested within region as a random effect. The within-patient correlation will be modeled using an unstructured covariance matrix in the mixed model. The Kenward-Roger approximation will be used to estimate denominator degrees of freedom (Kenward and Roger, 1997).

For the primary analysis, if the model does not converge, data only up to week 26 (i.e., Days 2 and 184) will be used (with unstructured covariance matrix). If still the model fails to converge, compound symmetry covariance matrix will be used. If model still does not converge, the random effects of center will be removed. For the final analysis, if the model does not converge with unstructured covariance matrix, the compound symmetry covariance matrix will be used in the mixed model. If still the model does not converge, the random effects of center will be removed. For both analyses, if the model converges after removing the random center effects, the original model without random center effects will be re-assessed. If the final model for the primary analysis converges without Week 52 data, only summary statistics will be provided for Week 52 data analysis. Restricted maximum likelihood method will be used.

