2.6.2.2 Spirometry data other than the primary endpoint

Trough FEV₁ at Day 2 and at Day 365 will be analyzed using the same MMRM as specified for the primary analysis and between-treatment comparison will be carried out using the adjusted mean (least-squares mean) difference based on the treatment main effect and the coefficient for the treatment-by-visit interaction corresponding to the respective visit. Adjusted mean (LS mean) will be displayed for each treatment group (for both the absolute FEV₁ value and the change from baseline value) along with the estimated treatment differences and the 95% confidence intervals and the two-sided p-values by visit.

In addition to trough FEV₁, pre-dose trough FEV₁ is defined as the average of the two FEV₁ measurements taken 45 min and 15 min pre-evening dose. Measurements will be done at Days 30, 86, 183, and 364. As for all spirometry data, measurements taken within 6 hours of rescue medication use or within 7 days of systemic corticosteroid use or within 3 months of a single depot corticosteroid injection will be set to missing. However, the post-evening dose time window of 22 – 25 hours or the post-morning dose time window of 8 – 13 hours cannot be applied here since the dosing data of the previous day or the morning of the day of pre-dose measurements will not be recorded. The same MMRM as for trough FEV₁ will be applied, however, with other visits included.

Post-dose FEV₁ measurements (5 min, 15 min, 30 min, 1 hr) will be analyzed separately by visit using the same MMRM as for trough FEV₁ with post-dose time point as repeat variable (i.e., in the MMRM, visit will be replaced by time point).

Pre- and post-dose FVC and FEF₂₅₋₇₅ will be analyzed similar to FEV₁.

To estimate the add-on effect of indacaterol to existing MF treatment (in terms of trough FEV₁), the average difference between QMF149 and MF will be computed across two dose levels. This difference is interpreted as an average effect of adding indacaterol to MF, under the assumption that indacaterol effect is not altered by dose of MF. To compute the difference, the QMF149 and MF doses will be pooled by averaging the following contrasts within the MMRM model, as specified for the primary analysis:

- QMF149 (150/160 µg) vs. MF 400 µg
- QMF149 (150/320 µg) vs. MF 800 µg.

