16.1.9.3 Assessment windows, baseline and post-baseline definitions, missing data handling

16.1.9.3.1 Data pooling and assessment windows

Data from unplanned or unscheduled visits or the early treatment/study discontinuation visits will be listed. For patients who do not complete the study, the treatment discontinuation visit will be an unscheduled visit.

Clinical laboratory measurements, vital signs and ECG data from unplanned or unscheduled visits will only be included in the summaries of the notable values and extreme values. All efficacy data (including spirometry data) from these visits will not be used for missing data imputation unless specified otherwise.

Laboratory, vital signs, and ECG values that have complete data and time values will be slotted into pre- or post-dose assessment based on the actual date/time. For values with missing date/time, scheduled visit date and time will be used. This rule will be applied to data from scheduled visits only. If a measurement scheduled as pre-dose is actually performed post-dose, or vice versa, the data will not be used for by time point assessments.

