As a sensitivity analysis to evaluate the impact of missing data, a tipping point analysis will be performed for the primary endpoint trough FEV₁ at Week 26. The delta-adjusting approach described in Ratitch et al (2013) will be used to find the tipping point, in a spectrum of conservative missing not at random (MNAR) assumptions, at which conclusions change from being favorable to QMF149 to being unfavorable. The basic idea is to first impute the missing Week 26 values using the multiple imputation (MI) method based on the MAR assumption. The imputed Week 26 values for the QMF149 arms are then adjusted by a delta value.

The endpoint is assumed to have a normal distribution at Day 2, Week 26 and Week 52. The primary analysis is performed on the delta-adjusted datasets to see if the conclusions change. If not, a larger delta is chosen and the process is repeated until the conclusion is overturned. The tipping point is the delta value which will cause the QMF149 vs. MF comparison on the primary endpoint to be no longer statistically significant. Different delta values are possible for QMF149 150/160 µg vs. MF 400 µg and QMF149 150/320 vs MF 800 µg. A series of analyses on a range of delta values will be performed to find the tipping point. For each delta value, the following steps will be performed.

1. Impute missing covariates (baseline FEV₁, FEV₁ prior to inhalation and FEV₁ 15 to 30 min post inhalation value) and missing values at Day 2 and/or Week 26 using the MI approach based on the fully conditional specification (FCS) method for 100 times and obtain 100 imputed datasets. Missing baseline FEV₁, FEV₁ prior to inhalation and FEV₁ 15 to 30 min post inhalation value will be imputed separately for each treatment group using a model with age group, geographic region, and the respective other covariates (baseline FEV₁, FEV₁ prior to inhalation and FEV₁ 15 to 30 min post inhalation value) as predictors. Missing Day 2 values will be imputed separately for each treatment group using a model with the imputed values of age group, geographic region, baseline FEV₁, FEV₁ prior to inhalation and FEV₁ 15 to 30 min post inhalation value as predictors. Missing Week 26 values will be imputed separately for each treatment group using a model with the imputed values of age group, geographic region, baseline FEV₁, FEV₁ prior to inhalation, FEV₁ 15 to 30 min post inhalation, and Day 2 value as predictors.

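### Missing Week 26 trough FEV1 is imputed with Day 2 as the only on-treatment predictor, although FEV1 at the same nominal time is collected at Days 30, 86 and 183 and left out

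*SAP*

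**What the plan says.** **Primary model.** SAP 2.6.1.2 fits a repeated-measures model with "visit (Days 2, 184, and 365), and treatment-by-visit interaction as fixed effects". Its covariates are baseline FEV1, the two reversibility FEV1 values, age group and region, with centre as a random effect. Trough FEV1 exists only on those days: "Trough measurements will be done at Day 2, Day 184 (Week 26, the primary endpoint) and Day 365". The same section makes the missing-at-random assumption conditional on the model taking account of the relevant observed data.

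**Imputation.** For the tipping point, SAP 16.1.9.6 step 1 states: "Missing Week 26 values will be imputed separately for each treatment group using a model with the imputed values of age group, geographic region, baseline". The last word there refers to the starting lung-function value; both reversibility values come next, and the list closes with "15 to 30 min post inhalation, and Day 2 value as predictors". Step 2 subtracts delta from imputed values in the QMF149 arms only.

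**FEV1 collected in between.** SAP 2.6.2.2 says "pre-dose trough FEV₁ is defined as the average of the two FEV₁ measurements taken 45 min and 15 min pre-evening dose" and "Measurements will be done at Days 30, 86, 183, and 364". These values are analysed in a separate secondary model.

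**Other data.** SAP 2.6 excludes off-treatment measurements from all efficacy analyses. For unscheduled and discontinuation visits, SAP 16.1.9.3.1 adds that "All efficacy data (including spirometry data) from these visits will not be used for missing data imputation unless specified otherwise".

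**Contrast within the SAP.** The ACQ-7 model includes every scheduled ACQ-7 visit, and the ACQ-7 responder imputation in 16.1.9.6 uses earlier post-baseline scores as predictors. Among these analyses, only the primary endpoint does without intermediate visits.

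**The concern.** The primary estimand (SAP 2.1.1) asks what a patient who stopped early would have had at Week 26 on treatment. The most informative evidence is that patient's last on-treatment FEV1. As planned, a patient who falls between Day 2 and Week 12 and then stops is predicted from pre-treatment values and Day 2, as if the fall had not been seen. A patient whose Day 184 trough is lost, for example through rescue use within 6 hours or a missed time window, has any valid Day 183 value set aside.

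Missing at random given Day 2 and the baseline covariates is a stronger assumption than missing at random given Weeks 4 and 12 as well. If stopping depends on interim decline and the arms differ in how many such patients they lose, the error does not cancel. It then enters both the primary difference and the delta = 0 starting point from which the tipping point is measured.

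**Working it through.** **1. Is the unused value at the same time point?** Trough FEV1 is "measured at 23 hr 15 min and 23 hr 45 min after the evening dose taken at the site" (Protocol 6.4.1). Pre-dose trough is taken at -45 and -15 min. For doses 24 h apart:
- 24 h - 45 min = 23 h 15 min
- 24 h - 15 min = 23 h 45 min

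The nominal times are identical. The actual times can differ, because home and clinic evening doses may each fall anywhere from 5 to 8 pm (Protocol 5.4.4). The dosing interval can therefore be up to 3 h shorter or longer than 24 h.

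**2. What each analysis uses before Week 26**

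| FEV1 value | Primary model | Imputation | Secondary pre-dose model |
|---|---|---|---|
| Baseline and reversibility | yes | yes | yes |
| Day 2 trough | yes | yes | no |
| Day 30, 86, 183 pre-dose | no | no | yes |

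**3. The plan's own planning figures.** The plan gives no figure on this point. Its planning inputs (SAP 2.10) are a difference of 100 mL, SD 380 mL, 400 per arm and 10% dropout, so 360 evaluable per arm.
- SE of the difference = 380 x sqrt(2/360) = 28.3 mL
- Power at two-sided 0.05 = 94.2%, against 94% stated

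These inputs reproduce and are used below.

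**4. Formula**
- Error in an arm mean = dropout fraction x (mean imputed - mean true Week 26 value among stoppers)
- Error in the contrast = QMF149 arm error - MF arm error

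The documents give no correlations between visits and no link between decline and stopping, so everything below is an assumption shown over a range.

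**5. Illustration A.** Dropout comes after Week 12, with log-odds rising 0.5 or 1.0 per SD of fall from Day 2 to Week 12. One case in full is autoregressive correlation 0.8 per visit, slope 1.0 and 10% dropout. Stoppers' true mean is -106.3 mL and the imputed mean is 89.9 mL, an excess of 196.2 mL each. Multiplied by about 0.10, this gives an arm error of about 19.7 mL. Across all settings:

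| Correlation | Slope | Arm error at 5% dropout (mL) | Arm error at 15% dropout (mL) | Contrast error, 5% v 15% (mL) |
|---|---|---|---|---|
| Exchangeable 0.5 | 0.5 | 2.4 | 7.0 | 4.6 |
| Exchangeable 0.5 | 1.0 | 4.6 | 13.0 | 8.4 |
| Exchangeable 0.7 | 0.5 | 2.6 | 7.6 | 5.0 |
| Exchangeable 0.7 | 1.0 | 5.0 | 13.9 | 8.9 |
| Autoregressive 0.7 | 0.5 | 5.0 | 14.7 | 9.7 |
| Autoregressive 0.7 | 1.0 | 9.7 | 27.4 | 17.7 |
| Autoregressive 0.8 | 0.5 | 5.3 | 15.6 | 10.3 |
| Autoregressive 0.8 | 1.0 | 10.1 | 28.7 | 18.6 |

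With Weeks 4 and 12 added as predictors, the arm error is at most 0.2 mL.

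**6. Illustration B.** Dropout comes after Week 12 and is driven by the Week 12 level (logistic slope 1 or 2). Correlations are 0.5 to 0.7 for Day 2/Week 26, paired with 0.7 to 0.85 for Week 12/Week 26. The true difference is 100 mL.

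| Dropout, MF/QMF149 | Estimate with Day 2 as only on-treatment predictor |
|---|---|
| 10%/10% | no bias |
| 13%/7% or 15%/5% | about 77 to 93 mL |
| 7%/13% | about 108 to 115 mL |
| 13%/7%, half of dropout decline-driven | about 92 to 97 mL |
| 15%/5%, half of dropout decline-driven | about 87 to 94 mL |

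Adding Weeks 4 and 12 returns about 100 mL. Pairing the correlations differently (0.5 with 0.85, or 0.7 with 0.7) widens the second row to about 72 to 95 mL.

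**7. Scale.** The shift in the second row is 7 to 23 mL. Against the planned SE that is 7/28.3 = 0.25 to 23/28.3 = 0.81 standard errors.

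**The case against.** **The prediction does not rest on Day 2 alone.** Baseline FEV1, both reversibility values, age group and region are also predictors, and the primary model adds centre and Day 365. This stands. The gap concerns on-treatment information only.

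**Day 2 is not a steroid-free value.** Patients enter on at least 3 months of inhaled steroid or low-dose combination and take fluticasone through run-in (Protocol 3.1). Calling Day 2 a response before any inhaled-steroid effect would be wrong.

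**Forced stopping is rare by design.** Protocol 5.4.9 requires a confirmed FEV1 fall above 50%, or five or more exacerbations treated with systemic steroids. A reader might infer that these rules generate much of the assumed 10% dropout; the documents do not show that.

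**The simulations favour the fix by construction.** All dropout falls after Week 12 and depends on Week 12, so adding Week 12 must repair it. Patients who stop before Week 4 gain nothing, and those who stop before Week 12 gain less. This stands, and the figures are illustrations only.

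**The tipping point already probes departures from missing at random.** This is partly true. It covers over-prediction in the QMF149 arms, which is the direction favourable to QMF149. It cannot correct over-predicted MF stoppers, does not use a patient's own course, and starts from a delta = 0 result with the same gap.

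**Pre-dose trough is a different variable.** Prior dosing times are not recorded, so the 22-25 h and 8-13 h windows cannot be applied. This is a good reason not to use it as the endpoint, and a weaker one against using it as a predictor.

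**Conclusion.** The point holds as a cheap improvement. Day 2 is the only on-treatment FEV1 informing a missing Week 26 value. Suitable values at Days 30, 86 and 183 are collected and unused, although the SAP ties its missing-at-random assumption to relevant observed data and uses earlier visits for ACQ-7.

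The size is conditional. In Illustration B, a true 100 mL reads as about 77 to 93 mL when more MF patients stop, about 108 to 115 mL when more QMF149 patients stop, and 100 mL when dropout is equal and equally related to decline. The error roughly halves if only half of dropout is decline-driven. All of this assumes the stated correlations and dropout after Week 12.

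Two stronger readings are not supported. One is that the primary result is biased: that needs unequal, decline-driven stopping, which the documents neither show nor exclude. The other is that the plan favours QMF149: the direction depends on which arm loses more declining patients, and if that is MF the omission works against QMF149.

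**What to change.** In SAP 16.1.9.6 step 1, add on-treatment pre-dose trough FEV1 at Days 30, 86 and 183 to the fully conditional specification as auxiliary predictors of Week 26. Apply the same steroid, rescue and implausible-value rules, and impute in visit order as is done for ACQ-7. Step 3 need not change, since an imputation model may hold more variables than the analysis model.

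Report the delta = 0 result beside the primary mixed model, which stays as it is. Small differences are expected anyway, because step 3 has neither the centre effect nor Day 365. A larger gap would suggest that the interim values matter.

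A supportive mixed model with Days 30 and 86 as extra visits is optional. It would mix window-checked and unchecked responses and enlarge the unstructured covariance matrix in a model that already has convergence fallbacks.

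The discontinuation-visit ACQ-7 should not be brought into the responder imputation as part of this change. That is a separate matter and may conflict with the off-treatment rule in SAP 2.6.

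The cost is a few lines of SAP text and code, with no new data. The drawbacks are a noisier predictor, because prior dosing times are unknown, and no gain for patients who stop before Week 4.

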2.6.1.3 Multiplicity adjustment

To control the family-wise type-I error rate at the two-sided 5% significance level, a multiple testing procedure based on the trimmed Simes test as described in Brannath et al (2009) will be used. The family for the overall type-I error rate control contains three hypotheses: two hypotheses for the primary endpoint trough FEV₁ and one hypothesis for the key secondary endpoint ACQ-7. Denote the two hypotheses for the primary endpoint as H1 and H2 for comparing QMF149 150/160 µg vs. MF 400 µg and QMF149 150/320 µg vs. MF 800 µg respectively. Similarly, denote the hypothesis as H3 for the key secondary endpoint ACQ-7, for comparing QMF149 vs. MF combined doses.

Below is a brief description of the testing procedure based on the trimmed Simes test in Brannath et al (2009).

Let p₁, p₂, p₃ be the corresponding p-values (2-sided) of the three hypotheses of H1, H2, and H3.

Step 1: Retain both H1 and H2 if p_i ≤ 0.05 **AND** the observed treatment difference for the corresponding p_i is in the wrong direction (i.e. MF is performing better than QMF) for **ANY** i = 1, 2, stop here; otherwise go to Step 2.

Step 2: Reject H1 and H2 if p_i < 0.05 for **BOTH** i=1, 2 and go to Step 3; otherwise go to Step 4.

Step 3: Reject H3 if p₃ < 0.05 and stop;

Step 4: If neither Step 1 nor 2 applies, perform the Bonferroni test to H1 and H2. Thus reject H1 if p₁ < 0.025 or reject H2 if p₂ < 0.025 and stop.

For each of the three hypotheses, the corresponding testing statistics (estimated least square mean difference) follows normal distribution. Hence for H1 and H2, their corresponding testing statistics follow jointly bivariate normal distribution. Therefore this testing procedure controls the overall type I error rate at the 2-sided 0.05 level in the strong sense regardless if the bivariate normal distributions have positive or negative correlations as shown in Brannath et al (2009).

Other than the 3 treatment comparisons mentioned above for the primary and the key secondary endpoint, all other analyses will be performed at the nominal 2-sided 0.05 level (2-sided) without multiplicity adjustment.

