2. After the imputation obtained in above step, for subjects in the two QMF149 treatment arms only, make the imputed value at Week 26 worse by a value of delta (i.e., subtract delta from the imputed value at Week 26). Note: delta = 0 represents the standard missing at random (MAR) based MI.
3. The final multiply-imputed dataset where all missing values are filled will be analyzed (by imputed dataset) using a linear model with treatment, age group, geographic region, baseline FEV₁, FEV₁ prior to inhalation, and FEV₁ 15 to 30 min post inhalation as predictors of trough FEV₁ at Week 26.
4. The results for the treatment effect from the 100 datasets will then be combined using Rubin's rule. If the combined results does not change the conclusion (i.e., the QMF149 treatment effect is still statistically significantly superior to MF), a larger delta will be chosen and Steps 1-4 will be repeated using the datasets from Step 1 until the tipping point is found (when $p > 0.05$).

- **Logistic regression analysis**

The proportions of patients who achieve a clinically relevant improvement in ACQ-7 (i.e., decrease of ACQ-7 score of at least 0.5 from baseline) at the scheduled post-baseline visits will be analyzed using logistic regression. The following steps will be performed for imputation of missing ACQ-7 data and following logistic regression analysis:

1. First, missing ACQ-7 values (continuous) at Visit 202, 204, 207, and 214 will be imputed sequentially using the MI method under MAR assumption. Missing values will be imputed separately for each treatment group using a model with age group (12 to 17, or ≥ 18 years), region, baseline ACQ value, FEV₁ prior to inhalation, FEV₁ within 15 to 30 min post inhalation of salbutamol/albuterol, and previous post-baseline ACQ-7 values as predictors for 100 times.
2. Continuous ACQ values will be converted into binomial responses (1 = an improvement of at least 0.5, 0 = no such improvement) and generalized estimating equation (GEE) method will be used to analyze the dataset (by imputed dataset). The GEE model will include terms for treatment, age group (12 to 17, or ≥ 18 years), region, visit, and treatment-by-visit interaction as fixed effects, and baseline ACQ-7, baseline-by-visit interaction, FEV₁ prior to inhalation and FEV₁ within 15 to 30 min post inhalation of salbutamol/albuterol (components of SABA reversibility) as covariates.

Combining results from 100 copies of original dataset:

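### The tipping-point search stops each dose at p > 0.05, but once one dose has tipped the SAP's own testing procedure requires p < 0.025 for the other

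*SAP*

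**What the plan says.** **Aim.** SAP 2.6.1.4 presents the tipping point as a sensitivity analysis showing what departure from missing at random would reverse the study's conclusions. SAP 16.1.9.6 repeats this: "If not, a larger delta is chosen and the process is repeated until the conclusion is overturned".

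**Search.** After multiple imputation, the instruction is: "for subjects in the two QMF149 treatment arms only, make the imputed value at Week 26 worse by a value of delta". Each completed dataset is analysed, the results are combined by Rubin's rule, and if significance remains "a larger delta will be chosen and Steps 1-4 will be repeated using the datasets from Step 1 until the tipping point is found". A parenthesis gives the stopping criterion as p > 0.05. The section also says: "Different delta values are possible for QMF149 150/160 µg vs. MF 400 µg and QMF149 150/320 vs MF 800 µg".

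**Decision rule under test.** SAP 2.6.1.3 (trimmed Simes) rejects both trough FEV1 hypotheses if both p-values are below 0.05. If not, and no dose is significantly worse than MF: "Step 4: If neither Step 1 nor 2 applies, perform the Bonferroni test to H1 and H2", with 0.025 for each. The same section places every analysis outside the three confirmatory comparisons at nominal two-sided 0.05.

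**Model.** SAP 16.1.9.6 states: "The primary analysis is performed on the delta-adjusted datasets to see if the conclusions change". The third step of the search, however, says the data "will be analyzed (by imputed dataset) using a linear model with treatment, age group, geographic region" and the FEV1 covariates.

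**The concern.** A tipping point is useful only if it marks the delta at which the reported decision changes. Here the decision for one dose depends on the p-value of the other. With a common delta and unequal estimates, the weaker comparison crosses 0.05 first, and from then on the stronger one is significant only if p < 0.025. The search goes on treating it as significant up to 0.05. For example, p = 0.03 for one dose with p = 0.20 for the other fails SAP 2.6.1.3 but counts as not yet tipped.

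The dose affected is the one still supporting the primary objective, which asks for superiority of either dose. What is at stake is a robustness figure that looks better than the decision it describes.

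**Working it through.** **Inputs** (SAP 2.10 and 2.6.1.3): difference 100 mL, SD 380 mL, 400 per arm, 10% dropout (360 evaluable), critical z 1.960 at 0.05 and 2.241 at 0.025. The SAP gives no tipping-point figure.

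**The plan's own figures first.** With 360 per arm, power for one comparison is 94.19% at 0.05 and 90.13% at 0.025. Under 2.6.1.3, per-dose power is P(p1 < 0.025) + P(0.025 ≤ p1 < 0.05) × P(p2 < 0.05) = 0.9013 + 0.0405 × 0.9419 = 0.9395, matching the stated 94%. Both doses succeed with probability 0.9419² = 0.887. ACQ-7 with 720 per pooled group, difference 0.15 and SD 0.80 has 94.5% power. Multiplied by 0.887 this is 83.8% if the endpoints are independent, close to the stated 85%. The inputs are therefore being read as the sponsor read them.

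**Tipping delta.** If a share f of an arm's Week 26 values is imputed and each is lowered by delta, the difference falls by f × delta. The comparison reaches critical value z when

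delta = (estimate − z × SE) / f, with SE = 380 × √(2 / (400 × (1 − f))).

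At f = 10%, SE = 380 × √(2/360) = 28.3 mL. The smallest significant difference is 1.960 × 28.3 = 55.5 mL at 0.05 and 2.241 × 28.3 = 63.5 mL at 0.025.

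**Correct value for the second dose.** It is the larger of (a) the first dose's tipping delta and (b) the delta at which the second dose's own p reaches 0.025. The SAP rule therefore exceeds it by

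min(difference between the two estimates, 0.281 × SE) / f.

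The maximum, 0.281 × SE / f, is:

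| Missing share | SE (mL) | Maximum overstatement (mL) |
|---|---|---|
| 10% (planned) | 28.3 | 80 |
| 15% (assumed) | 29.1 | 55 |
| 20% (assumed) | 30.0 | 42 |

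**Examples at 10% missing.**
- Estimates 90 and 110 mL: the weaker dose tips at (90 − 55.5)/0.10 = 345 mL. The stronger tips at (110 − 55.5)/0.10 = 545 mL by the search rule, but at (110 − 63.5)/0.10 = 465 mL under 2.6.1.3. The overstatement is 80 mL, or 17%.
- Both estimates 100 mL: both tip at (100 − 55.5)/0.10 = 445 mL and nothing is overstated.
- One estimate 100 mL: the full gap, 365 against 445 mL, needs the other dose at or below about 92 mL, since (92 − 55.5)/0.10 = 365.

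**How often.** Estimates were simulated independently around 100 mL with SE 28.3 mL. The full 80 mL applied in about 83% of trials where both doses were significant.

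**Approximation.** These figures hold SE fixed as delta grows. Allowing for the variance that the shift adds gives 76 mL instead of 80 mL at 10% missing.

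**One dose only.** If just one dose was significant in the primary analysis, through the 0.025 step, the other already has p ≥ 0.05 at delta = 0. The 0.05 stop is then too lenient throughout, by the full amount.

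**The case against.** The strongest reply is that 0.05 follows a stated rule: SAP 2.6.1.3 assigns nominal 0.05 to everything outside the three confirmatory comparisons, and this is a sensitivity analysis. SAP 16.1.9.6 also defines the tipping point for each comparison by loss of statistical significance. That explains the choice and means no rule is broken. It does not make the result match the study conclusion that the analysis says it is testing.

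Second, the permission for different deltas by dose may mean that each arm is shifted alone. If the unshifted dose keeps p < 0.05, then 0.05 is the right threshold for the shifted one. A single delta subtracted in both QMF149 arms is the plainer reading, but the text does not exclude the other.

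Third, 365 and 445 mL are both about one SD (380 mL) and roughly four times the planned effect, so clinical judgement might treat them alike. That limits the practical importance.

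Three stronger readings are tempting and not supported:
- *Type I error is inflated.* The search makes no confirmatory claim, so the procedure in 2.6.1.3 is untouched.
- *The point at which ACQ-7 testing closes is hidden.* With a common delta, that gate closes when either dose reaches p ≥ 0.05, which is the smaller tipping point and is already found correctly.
- *Step 3 uses a wrong model.* The SAP says delta = 0 is standard multiple imputation under missing at random and does not promise to reproduce the MMRM. A single-visit model is a normal choice when Day 2 has served as a predictor in the imputation. What remains is a loose phrase and the absence of a centre effect.

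**Conclusion.** The point holds in a limited form. With a common delta, the search gives the correct tipping point for the dose that tips first and can overstate that of the dose that tips second. It also overstates that of a sole dose won at 0.025. At the planned 10% missing the excess ranges from zero (equal estimates) to about 80 mL, reaching the maximum once the estimates differ by about 8 mL (0.281 × 28.3). In the 90/110 mL example that is 17% of the correct value.

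The size rests on the planning SD, equal missing shares in the arms compared, and f equal to the 10% dropout. SAP 2.6.1.1.1 also sets values to missing for rescue use, corticosteroids and timing, so f may be larger, which makes the excess smaller in mL. This is a worthwhile refinement of a supportive analysis. It does not threaten the primary result.

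**What to change.** In SAP 16.1.9.6:

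1. State whether delta is common to both QMF149 arms or varied by arm.
2. At each delta, or each pair of deltas on a two-way grid, apply the whole of SAP 2.6.1.3 to (p1, p2), including its first step, which retains both hypotheses if a dose is significantly worse than MF.
3. Define each dose's tipping point as the smallest delta at which that procedure no longer rejects its hypothesis, and report the delta at which the either-dose conclusion is lost.
4. Reword the sentence saying that the primary analysis is run on the adjusted data so that it names the linear model of the third step, and show the delta = 0 result beside the primary MMRM.

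The cost is some wording and a few lines of code, with no new data. The downside for the sponsor is a slightly less favourable tipping point for the second dose.
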